10.3.3.3. Other Secondary and Tertiary Analyses

There will be no adjustments for multiplicity for analyses of the other secondary or tertiary endpoints not listed in Figure CGAW.2. The analysis models are described in Section 10.3.1.

10.3.4. Safety Analyses

The safety and tolerability of treatment will be assessed by summarizing the following:

- TEAEs
- SAEs
- AEs leading to discontinuation
- potential hypersensitivity events
- AEs related to injection sites
- vital signs and weight
- ECGs

laboratory measurements

Unless specified otherwise, the categorical safety analyses will include both scheduled and unscheduled visits. Comparisons between treatment groups for all categorical safety measures will be made using Fisher's exact test for Study Period III with the safety population. Descriptive statistics only will be presented for the analyses in Study Period IV.

Analyses of continuous safety data will be conducted for Study Period III and Study Period III/IV using the safety population. In those analyses, only values collected at scheduled visits will be used.

10.3.4.1. Treatment-Emergent Adverse Events

Treatment-emergent adverse events are defined as the reported AEs that first occurred or worsened during the postbaseline phase compared with the baseline phase. For each TEAE, the reported severity level of the event (mild, moderate, or severe) will be determined by patient or physician opinion. The Medical Dictionary for Regulatory Activities (MedDRA) Lowest Level Term (LLT) will be used in the treatment-emergent computation. For each LLT, the maximum severity at baseline will be used as the baseline severity. If the maximum severity during postbaseline is greater than the maximum baseline severity, the event is considered to be treatment-emergent for the specific postbaseline period. Safety analyses for each study period will use all visits up through the last scheduled visit in the prior study period as baseline. For each patient and TEAE, the maximum severity for the MedDRA level being displayed (preferred term, High Level Term, or SOC) is the maximum postbaseline severity observed from all associated LLTs mapping to that MedDRA level.

For events that are sex-specific, the denominator and computation of the percentage will include only patients from the specific sex.

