9.2. Adverse Events

Investigators are responsible for monitoring the safety of patients who have entered this study and for alerting Lilly or its designee to any event that seems unusual, even if this event may be considered an unanticipated benefit to the patient.

The investigator is responsible for the appropriate medical care of patients during the study.

Investigators must document their review of each laboratory safety report and ECG.

The investigator remains responsible for following, through an appropriate health care option, AEs that are serious or otherwise medically important, considered related to the investigational product or the study, or that caused the patient to discontinue the investigational product before completing the study. The patient should be followed until the event resolves, stabilizes with appropriate diagnostic evaluation, or is reasonably explained. The frequency of follow-up evaluations of the AE is left to the discretion of the investigator.

Lack of drug effect is not an AE in clinical studies, because the purpose of the clinical study is to establish treatment effect. However, any worsening of the primary study condition should be recorded as an AE

After the ICF is signed, study site personnel will record via eCRF the occurrence and nature of each patient's pre-existing conditions, including clinically significant signs and symptoms of the disease under treatment in the study. In addition, site personnel will record via eCRF any change in the condition(s) and any new conditions as AEs. Investigators should record their assessment of the potential relatedness of each AE to protocol procedure or investigational product via eCRF.

The investigator will interpret and document whether or not an AE has a reasonable possibility of being related to study treatment, study device, or a study procedure, taking into account the disease, concomitant treatment, and pathologies.

A "reasonable possibility" means that there potentially is a cause and effect relationship between the investigational product, study device, and/or study procedure and the AE.

The investigator will answer yes or no when making this assessment.

The investigator will use AE follow-up forms to record additional details regarding AEs related to injection sites and hypersensitivity events.

Planned surgeries and nonsurgical interventions should not be reported as AEs unless the underlying medical condition has worsened during the course of the study.

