5.5.4. Patient Characteristics

The following patient characteristics at baseline will be summarized by treatment group.

- Demographic (age, sex, ethnic origin, height, weight, BMI)
- Migraine and/or headache measures per 30-day baseline period:
 - o number of migraine headache days
 - o number of ICHD migraine headache days
 - o number of headache days
 - o number of migraine headache hours
 - number of headache hours
 - o number of migraine attacks
 - o number of monthly days with abortive medication use
 - o number of migraine headache days with nausea and/or vomiting
 - o number of migraine headache days with photophobia and phonophobia

- o number of migraine headache days with aura
- o number of migraine headache days with prodromal symptoms other than aura
- Number of prior migraine preventive medication categories failed in the past 10 years: 2, 3, or 4
- Patient Global Impression Severity
- Alcohol, tobacco, caffeine, and nicotine consumption
- Medical history and preexisting conditions
- Presence of aura at baseline
- CCI
- CC
- Contraindications to migraine preventive medications

Comparisons between treatment groups will be performed using Fisher's exact test for categorical data and ANOVA with treatment as independent variable in the model for continuous data.

Medical history and preexisting conditions will be summarized by descending frequency of preferred term (PT) within system organ class (SOC), and comparison between treatment groups will be performed using Fisher's exact test. Medical history is defined as illness(es) that ended prior to the signing of informed consent. Preexisting conditions and AEs at baseline are those AEs occurring during the baseline/screening visits for the study period, that is, Visit 1, Visit 2, and Visit 3.

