5.5.12. Safety Analyses

Unless specified otherwise, safety analyses outlined in the following subsections will be conducted on the safety population for SP III and on the GMB-treated population during the GMB-treated time; for SP III/IV, only the change from baseline with MMRM analysis will be conducted.

The safety and tolerability of treatment will be assessed by summarizing the following:

- Treatment-emergent adverse events (TEAEs)
 - o By preferred term (PT)
 - o By PT nested within system organ class (SOC)
 - o By maximum severity
 - o By considered to be related to investigational product by investigator
- Serious adverse events (SAEs) by PT
- AEs leading to discontinuation by PT
- Vital signs and weight

- Laboratory measurements
- ECGs

Additionally, TEAEs by PT will be conducted on the open-label population for SP IV only.

The baseline and postbaseline for all safety measures are described in Table CGAW.5.4 unless specified otherwise.

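### The displayed severity of a TEAE is not limited to treatment-emergent LLTs, so a non-emergent LLT under the same term can raise it

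*Protocol*

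**What the plan says.** Protocol 10.3.4.1 works in two steps, and SAP 5.5.12.1.1 repeats both.

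- **Emergence, per LLT.** The "Lowest Level Term (LLT) will be used in the treatment-emergent computation". The baseline reference is also per LLT: "For each LLT, the maximum severity at baseline will be used as the baseline severity". The condition is a strict increase: "If the maximum severity during postbaseline is greater than the maximum baseline severity, the event is considered to be treatment-emergent". An LLT that is equally severe before and after baseline is therefore not treatment-emergent.
- **Severity, per displayed level.** Once a patient has a TEAE, the severity tabulated for it at PT, HLT or SOC "is the maximum postbaseline severity observed from all associated LLTs mapping to that MedDRA level".

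The rule feeds a planned output. SAP 5.5.12 lists TEAEs "By maximum severity" for the safety population in Study Period III and for the galcanezumab-treated population over galcanezumab-treated time. The hypersensitivity and injection-site sections of the SAP also plan TEAE tables by maximum severity, both at PT level.

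Baseline records include existing disease. Under Protocol 9.2, sites record "pre-existing conditions, including clinically significant signs and symptoms of the disease under treatment in the study". SAP 5.5.4 groups these with baseline events: "Preexisting conditions and AEs at baseline are those AEs occurring during the baseline/screening visits for the study period".

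**The concern.** The two steps use different sets of LLTs. The first excludes any LLT that did not worsen. The second takes its maximum over every LLT that maps to the displayed term, which on its face brings the excluded LLTs back in. The severity shown for a TEAE can then come from an event that the plan itself has classed as not treatment-emergent.

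The stake is how to read the severity columns. A TEAE table by maximum severity should describe the treatment-emergent events. As written, a moderate or severe entry may describe something the patient already had at that severity. Two programmers could also follow the same sentence and produce different tables.

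**Working it through.** The plan states no figure on this point, so there is none to reproduce. The check is of the rule itself.

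**Inputs.** Severity is coded 0 none, 1 mild, 2 moderate, 3 severe. B is the maximum baseline severity of an LLT and P its maximum postbaseline severity. The emergence condition P > B and the severity rule are those of Protocol 10.3.4.1 and SAP 5.5.12.1.1.

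**The two rules.**
- As written: S = max of P over all LLTs under the term.
- Restricted: S_TE = max of P over LLTs with P > B.

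The second maximum is over a subset of the first, so S ≥ S_TE always. Any discrepancy is upward. The two agree when the term holds only one LLT, or when every LLT with a postbaseline severity is treatment-emergent.

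**Enumeration for two LLTs under one term.** Each LLT has 4 × 4 = 16 (B, P) pairs, of which 6 have P > B and 10 do not. Patterns with at least one treatment-emergent LLT: 16 × 16 − 10 × 10 = 156. The rules differ only when one LLT is emergent and the other is not, and the non-emergent one has the higher P.
- Emergent pairs by P: one with P = 1, two with P = 2, three with P = 3.
- Non-emergent pairs by P, where it matters: two with P = 2, one with P = 3.

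| Restricted rule | As written | Patterns (× 2 because either LLT can be the emergent one) |
|---|---|---|
| mild | moderate | 1 × 2 × 2 = 4 |
| mild | severe | 1 × 1 × 2 = 2 |
| moderate | severe | 2 × 1 × 2 = 4 |
| **Total differing** | | **10 of 156** |

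The written rule is higher in all 10. The extreme case is one LLT going from none to mild beside another that is severe before and after: the table shows severe, and the restricted rule shows mild. These are counts of possible patterns, not expected frequencies.

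**How a non-emergent LLT can have a postbaseline severity.**
1. A condition present at baseline is carried forward as ongoing with a severity grade.
2. An event recurs. In SAP Table CGAW.5.4, the galcanezumab-treated-time baseline for patients first given placebo covers Visits 1 to 6 before open-label dosing. An event from the placebo period is then a baseline event. If it recurs after the switch at equal severity, it is not treatment-emergent, yet it has a postbaseline severity.

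**Level of display.** At PT, the effect needs two different LLTs of the same PT, one emergent and one not. At HLT or SOC many more LLTs share a term, so the coincidence is more likely.

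**The case against.** **The narrower reading.** The severity sentence is framed per patient and TEAE, and a TEAE is defined per LLT. Associated LLTs could therefore mean only the LLTs that make up that TEAE, and the program may already work this way. This stands in part: inclusion of non-emergent LLTs follows from the word all and the absence of a qualifier, and is not stated outright. But the sentence identifies the LLTs by where they map in the dictionary, not by emergence, and nothing elsewhere narrows it.

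**The data may not be there.** After recording pre-existing conditions, Protocol 9.2 asks sites to record changes and new conditions as AEs. It does not say that an unchanged condition is graded again. This stands: an unchanged condition contributes only if it is carried forward with a severity. The objection does not reach the recurrence route, where the later event is itself recorded.

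**No SOC-level severity table is named.** SAP 5.5.12 gives no level for its maximum-severity table. Where the SAP does give a level, for hypersensitivity and injection-site events, it is PT. Those two tables are little exposed. Hypersensitivity terms also pass a medical review before tabulation, and a graded injection-site event before the first study injection is unlikely. The protocol rule does allow for HLT and SOC.

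**Stronger inferences a reader might draw.**
- *That background migraine fills the severe column.* With 210 patients per arm (420/2), suppose 10% have a nervous system TEAE (21 patients), 5% of those are truly severe, and a share q carry a non-emergent severe LLT in that SOC. The table then shows 21 × (0.05 + 0.95q) severe patients, against 21 × 0.05 = 1.05. For q = 0.01, 0.05, 0.20 and 0.60 this is about 1.2, 2.0, 5.0 and 13.0. The answer is driven almost wholly by q, for which the documents give no value, and by a SOC-level table that they do not specify.
- *That the rule favours galcanezumab, because migraine severity may fall on active drug.* This would need migraine to be graded repeatedly as an AE record, displayed at SOC, and improved differently by arm. The documents establish none of these as part of the severity tabulation.

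**Conclusion.** The wording gap is real and is in both documents. Read literally, the rule lets an LLT that is not treatment-emergent set the displayed severity of a TEAE arising from another LLT under the same term. The direction is certain: it can only raise severity, and it can do so in either arm. The size cannot be derived from the documents. It depends on how ongoing conditions are carried forward, how often events recur at equal severity, and the MedDRA level of the table.

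The reach is narrow. Only the severity category changes. Whether a patient counts as having a TEAE, the SAE and discontinuation counts, and all efficacy results are unaffected. The documents do not support a claim of bias toward galcanezumab or any particular percentage of mislabelled patients. The conclusion assumes that the sentence is programmed as it reads. If the program already filters on emergence, only the text needs correcting.

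**What to change.** In SAP 5.5.12.1.1, insert the word treatment-emergent between associated and LLTs in the severity sentence. Make the same insertion in Protocol 10.3.4.1 if the protocol is amended for another reason. Protocol 10.3.1 and SAP 5.5.1 allow changes of analysis method that do not touch a principal feature to be described in the SAP or the clinical study report, so this should not need its own amendment.

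Confirm that the maximum-severity program keeps only LLTs with P > B before taking the maximum, for Study Period III and for galcanezumab-treated time, and that the hypersensitivity and injection-site severity tables use the same filter. State the MedDRA level of the main maximum-severity table at the same time.

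The cost is one qualifier and one program filter, with no new data. Severity counts can only stay the same or move to lower categories.

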10.3.4.2. Vital Signs

Vital signs collected during the study include systolic and diastolic blood pressure, pulse, and temperature. Blood pressure and pulse measurements will be taken when the patient is in a sitting position.

The number and percentage of patients meeting criteria for treatment-emergent abnormalities in vital signs and weight at any time during study will be summarized. Treatment group comparisons will be performed using Fisher's exact test.

10.3.4.3. Electrocardiogram Intervals and Heart Rate

The corrected QT interval will be calculated using the Fridericia method (QTcF). The number and percentage of patients meeting criteria for treatment-emergent abnormalities in ECG intervals (pulse, QRS, and QTcF) and heart rate at any time during study will be summarized. Treatment group comparisons will be performed using the Fisher's exact test.

10.3.4.4. Laboratory Tests

The incidence rates of patients with treatment-emergent abnormal, high, or low laboratory values at any time postbaseline will be assessed using Fisher's exact test for each laboratory test.

Patients will be defined as having a treatment-emergent low value if they have all normal or high values at baseline, followed by a value below the lower reference limit at any postbaseline visit. Patients with all normal or high values at baseline (no low values) will be included in the analysis of treatment-emergent low laboratory values. Patients will be defined as having a treatment-emergent high value if they have all normal or low values at baseline, followed by a value above the upper reference limit at any postbaseline visit. Patients with all normal or low values at baseline (no high values) will be included in the analysis of treatment-emergent high laboratory values.

For analytes simply classified as normal or abnormal, patients will be defined as having a treatment-emergent abnormal value if they have all normal values at baseline, followed by an abnormal value at any postbaseline visit. Patients with all normal values at baseline will be included in the analysis of treatment-emergent abnormal laboratory values.

10.3.5. Health Economics

The change from baseline for the double-blind treatment phase and for the open-label treatment phase for MSQ v2.1 (Role Function-Restrictive, Role Function-Preventive, and Emotional Function domains and total score), MIDAS (item scores and total score), EQ-5D-5L, MIBS-4, WPAI questionnaire, CCI will be analyzed. In addition, categorical analyses will be performed. Changes in health care resource utilization and employment status will also be evaluated. Details are summarized in the SAP.

10.3.6. Subgroup Analyses

Subgroup analyses for the primary efficacy measure of change from baseline in the number of monthly migraine headache days will include the following subgroup variables:

- sex
- racial origin
- age
- migraine headache day frequency categories (high frequency episodic migraine, low frequency episodic migraine, or chronic migraine)
- number of failed preventive migraine medication categories (2, 3, or 4)
- geographical region

Additional details are available in the SAP.

10.3.7. Interim Analyses

An interim analysis will be conducted after all patients have had the opportunity to complete Study Period III, and thus will be the final analysis of the primary efficacy endpoint.

Study sites, patients, and all Lilly personnel directly involved in the continuing trial will remain blinded to patients' double-blind treatment assignment. Unblinding details are specified in the unblinding plan section of the SAP or a separate unblinding plan document.

No other interim analyses are planned for this study. If an unplanned interim analysis is deemed necessary, the appropriate Lilly medical director or designee will be consulted to determine whether it is necessary to amend the protocol.

11. References

Appendix 1. Abbreviations and Definitions

Term	Definition
ADA	anti-drug antibodies
AE	adverse event: Any untoward medical occurrence in a patient or clinical investigation subject administered a pharmaceutical product that does not necessarily have a causal relationship with this treatment. An adverse event can therefore be any unfavorable and unintended sign (including an abnormal laboratory finding), symptom, or disease temporally associated with the use of a medicinal (investigational) product, whether or not related to the medicinal (investigational) product.
ALP	alkaline phosphatase
ALT	alanine aminotransferase
ANCOVA	analysis of covariance
AST	aspartate aminotransferase
blinding/masking	A single-blind study is one in which the investigator and/or his staff are aware of the treatment but the patient is not, or vice versa, or when the sponsor is aware of the treatment but the investigator and/his staff and the patient are not.
	A double-blind study is one in which neither the patient nor any of the investigator or sponsor staff who are involved in the treatment or clinical evaluation of the patients are aware of the treatment received.
CGRP	calcitonin gene-related peptide
complaint	A complaint is any written, electronic, or oral communication that alleges deficiencies related to the identity, quality, purity, durability, reliability, safety or effectiveness, or performance of a drug or drug delivery system.
compliance	Adherence to all study-related, good clinical practice (GCP), and applicable regulatory requirements.
DSM-5	Diagnostic and Statistical Manual of Mental Disorders, Fifth Edition
DSM-IV	Diagnostic and Statistical Manual of Mental Disorders, Fourth Edition
ECG	electrocardiogram
eCRF	electronic case report form
enroll	The act of assigning a patient to a treatment. Patients who are enrolled in the study are those who have been assigned to a treatment.

enter Patients entered into a study are those who sign the informed consent form directly or

through their legally acceptable representatives.

ePRO electronic patient-reported outcomes

EQ-5D-5L European Quality of Life 5-Dimensions 5-Levels

ERB ethical review board

CCI

GCP good clinical practice

HCRU Health Care Resource Utilization questionnaire

IB Investigator's Brochure

ICF informed consent form

ICHD-3 International Classification of Headache Disorders – 3rd edition

IHS International Headache Society

Informed consent A process by which a patient voluntarily confirms his or her willingness to participate

in a particular study, after having been informed of all aspects of the study that are relevant to the patient's decision to participate. Informed consent is documented by

means of a written, signed and dated informed consent form.

interim analysis An interim analysis is an analysis of clinical study data, separated into treatment groups,

that is conducted before the final reporting database is created/locked.

investigational

product

A pharmaceutical form of an active ingredient or placebo being tested or used as a reference in a clinical trial, including products already on the market when used or assembled (formulated or packaged) in a way different from the authorized form, or marketed products used for an unauthorized indication, or marketed products used to

gain further information about the authorized form.

intent to treat: The principle that asserts that the effect of a treatment policy can be best

assessed by evaluating on the basis of the intention to treat a patient (that is, the planned treatment regimen) rather than the actual treatment given. It has the consequence that patients allocated to a treatment group should be followed up, assessed, and analyzed as members of that group irrespective of their compliance to the planned course of

treatment.

IWRS interactive web-response system

LOCF last observation carried forward

LSMean Least Squares Mean

MDD major depressive disorder

MIBS-4 4-item Migraine Interictal Burden Scale

MIDAS Migraine Disability Assessment

MMRM mixed model repeated measures

MSQ (v2.1) Migraine-Specific Quality of Life Questionnaire version 2.1

PGI-S Patient Global Impression of Severity

CCI

QTcF Fridericia's corrected QT interval

SAE serious adverse event

SAP statistical analysis plan

Screen The act of determining if an individual meets minimum requirements to become part of

a pool of potential candidates for participation in a clinical study.

SOC system organ class

SUSARs suspected unexpected serious adverse reactions

TBL total bilirubin

TEAE treatment-emergent adverse event: An untoward medical occurrence that emerges

during a defined treatment period, having been absent pretreatment, or worsens relative to the pretreatment state, and does not necessarily have to have a causal relationship

with this treatment.

ULN upper limit of normal

VAS visual analog scale

WPAI Work Productivity and Activity Impairment Questionnaire

